### **11.3. Video Evidence**

Clinical assessments required at each study visit will be videotaped in an effort to produce compelling, demonstrable, documented evidence of efficacy, as determined by changes in functional abilities. AveXis will provide a secure and confidential upload process for transfer and storage of the videos from investigational sites to a contracted third-party vendor that will compile and arrange videos as per AveXis requirements. Any/all videos received at AveXis or the contracted vendor will be treated as confidential study data and will be the sole property of AveXis. AveXis and the contracted vendor will provide this secure, encrypted transfer and storage solution to properly protect the identities of patients/families on the videos, which may be shared with regulatory agencies and/or the medical community, and/or in appropriate venues to discuss the results of this clinical trial.

Videos will be provided to an independent, centralized reviewer for unbiased assessment of milestone achievement. The independent central reviewer will document whether the video displays evidence of having achieved each developmental milestone. The date of motor milestone achievement will be computed as the earliest date on which video evidence demonstrates the achievement of the specified developmental milestone.

Additionally, the parent(s)/legal guardian(s) may submit additional videos demonstrating achievement of developmental milestones at any time during the trial. These videos will be handled in the same manner in which the trial-derived videos are handled.

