### 14.2. General

Binary endpoints (e.g., standing without support) will be compared between AVXS-101 and natural history control groups using a 2-sided Fisher's Exact Test at level of 0.05. A 95% exact unconditional confidence interval for the true population difference in response rates will be computed.

Results involving continuous endpoints (e.g., change in HFMSE) will be compared between AVXS-101 and natural history control groups at 2-sided significance level  $\alpha=0.05$  using analysis of variance (ANOVA), or non-parametric Wilcoxon Rank Sum test, as appropriate.

All statistical tests will be conducted at a significance level of 0.05.

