The primary efficacy endpoint for the group of patients  $\geq$  6 months and  $<$  24 months of age at time of dosing will be the proportion of patients who achieve the ability to stand alone up to the 12-month study visit. Twenty-four (24) children aged  $\geq$  6 months and  $<$  24 months will be enrolled, with twelve (12) children receiving Dose B and twelve children receiving Dose C. The proportion of patients developing the ability to stand alone will be compared with a cohort of eligibility-matched patients from the PNCR natural history study of SMA; this comparison will be conducted for Dose B only. Based upon a review of eligibility-matched patients from the PNCR, fourteen percent (14%) of patients who meet the study criteria for patients  $\geq$  6 months and  $<$  24 months of age achieved the ability to stand alone, and ten percent (10%) achieved the ability to walk alone. It is expected that 85% of treated patients  $\geq$  6 months and  $<$  24 months of age will achieve the ability to stand alone and 60% will achieve the ability to walk alone. With this efficacy, a sample size of 12 patients would provide power of  $>$  90% to detect a significant difference compared with the matched control cohort with  $\alpha = 0.05$  using a two sample 2-sided Fisher exact test.

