## 4. ENDPOINTS

### 4.1. Primary Efficacy Endpoints

Primary efficacy endpoints are assessed independently for each age group and for each dose separately. As detailed in Section 3.4.1 of this SAP, Dose A and Dose C will each be summarized descriptively and will not be compared to the historical data of the PNCR network. Assessment of developmental milestones will be determined by the clinical evaluator (CE) at the investigative sites. The primary source for developmental milestone data will be based on documented video evidence captured by site CE or patient families that is reviewed and concurred by an independent central reviewer.

- Patients  $\geq$  6 months and  $<$  24 months at time of dosing:

The primary efficacy endpoint is the proportion of treated patients who achieve the ability to stand alone (Bayley-III – Gross Motor Subtest item # 40) at any post-treatment visit up to the 12-month study visit.

- Patients  $\geq$  24 months and  $<$  60 months at time of dosing:

The primary efficacy endpoint is the change from baseline in HFMSE in treated patients at the 12-month study visit.

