## 5.6. PNCR Population-Matched Control Population

A population-matched control cohort will be drawn from the PNCR Natural History dataset. The PNCR is a large natural history study developed from a cohort of 337 patients with any form of spinal muscular atrophy followed at 3 large, internationally recognized tertiary medical centers with significant expertise in the management of SMA (Harvard University/Boston Children's Hospital, Columbia University and the University of Pennsylvania/Children's Hospital of Philadelphia).

Previously identified patients with any form of SMA, of any age, followed in PNCR site clinics and newly diagnosed patients were enrolled. All eligible patients were offered participation. Study visits were scheduled at baseline and at 2, 4, 6, 9, and 12 months and every 6 months thereafter. The SMA standard of care guidelines published in 2007 were used as a basis for providing uniform care among the study sites.

For purposes of this study, sitting (for SMA-II) was defined as being able to sit independently for > 10 seconds, and walking alone was defined as having scored 2 points on item #20 of the HFMSE at any time. All patients with SMA type 2 or 3 who provided sufficient records and follow-up for evaluation and met the basic entry criteria for the two cohorts of the AVXS-101-CL-102 study (3 copies of *SMN2*, symptom onset before 12 months of age and baseline and follow-up visits within the age criteria for the study) were considered for possible inclusion in the natural history comparison dataset. The *SMN2* modifier mutation (c.859G>C) described by Prior and colleagues (Prior et al., 2009) was not assessed in the PNCR study cohort.

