### 5.6.1. Primary analyses vs. PNCR

For the cohort of patients  $\geq$  6 months and  $<$  24 months of age, patient-level data from a cohort of 51 patients drawn from the PNCR Network natural history study of SMA will serve as a “population-matched” control cohort. This comparison cohort encompasses all 51 patients enrolled in the PNCR study who met the criteria of having SMA Types 2 or 3, 3 copies of *SMN2* and symptom onset before 12 months of age and had at least one visit at or before 36 months of age. Of this cohort, 7/51 (14%) of the natural history cohort attained the ability to stand alone (defined as achieving a score of 2 on item #19 of the HFMSE). 5/51 (10%) attained the ability to walk alone (defined as achieving a score of 2 on item #20 of the HFMSE).

For the cohort of patients between 24 and  $<$  60 months of age, patient-level data from a cohort of 15 patients drawn from the PNCR Network natural history study of SMA will serve as a “population-matched” control cohort for the primary analysis. This comparison cohort encompasses all 15 patients enrolled in the PNCR study who met the criteria of having SMA Types 2 or 3, 3 copies of *SMN2*, symptom onset before 12 months of age, diagnosis before 24 months of age and unable to stand or walk at enrollment (baseline visit) and who received a HFMSE evaluation between 24 and 60 months of age (“baseline”), and a follow-up evaluation

(HFMS or HFMSE) performed between 12 and 14 months following that baseline evaluation. It is stated in the protocol that among the patients in this cohort, a mean change of -1.33 points (Standard deviation=4.32) was seen in HFMS. However, the primary endpoint for this cohort is HFMSE, not HFMS. As such, the comparison to PNCR will utilize HFMSE. Among patients in this PNCR cohort, a mean change of -1.13 points (Standard deviation=4.90) was seen in HFMSE, in line with other publications describing disease progression in SMA type 2 and 3 patients (Kaufman et al 2012, Mercuri et al 2016). From this point forward, this PNCR comparator group of 15 patients will be referred to as the “Primary PNCR” group.

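### Milestones can be seen more often and are dated earlier in treated children than in PNCR children; the bias is clearest in the Cox comparisons, and the net direction is not established

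*Protocol*

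**What the plan says.** **Treated children.** The Schedule of Assessments (Protocol Table 3) and SAP Table 4.1 give monthly motor assessments, so 12 post-baseline occasions to Month 12. Protocol 11.3 also provides that "the parent(s)/legal guardian(s) may submit additional videos demonstrating achievement of developmental milestones at any time during the trial". SAP 4.1 takes as the primary source "documented video evidence captured by site CE or patient families that is reviewed and concurred by an independent central reviewer", and SAP 6.4.3 likewise accepts video taken outside the site. Under Protocol 11.2 one showing is enough, and Bayley items need not be repeated once attained. Protocol 11.3 dates attainment to the earliest video that shows it, whereas Protocol 11.2 dates it to the visit at which it is observed.

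**PNCR children.** SAP 5.6 states: "Study visits were scheduled at baseline and at 2, 4, 6, 9, and 12 months and every 6 months thereafter". SAP 8.1.1 and 8.2.1 credit a PNCR child who scores 2 on the relevant HFMSE item at Baseline or at any visit within 12 months of it. No home-video source and no central video review are described for them. SAP 6.5 re-maps PNCR children whose Baseline value is missing; in its worked example the post-baseline looks fall at Months 2, 5 and 8 only.

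**Comparisons.** Fisher tests compare the proportions, and Cox models with study day as the time variable compare time to standing (SAP 8.1.1) and time to walking (SAP 8.2.1).

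**The concern.** Standing in the younger group (primary) and walking in both age groups (secondary) are outcomes of the ever-shown kind. More looks, and a second route through family video, can only raise the treated count and bring treated dates forward. The comparison would then partly measure how closely children were watched.

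No planned analysis addresses this. The Per Protocol and completer analyses change who is included, not how milestones are captured. The optional COVID-19 analysis of proportions extends the treated window by up to three months past day 374 and describes no matching extension for PNCR.

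**Working it through.** **Inputs from the documents (younger group).** Alpha: "All statistical tests will be conducted at a significance level of 0.05" (Protocol 14.2). Test: "using a two sample 2-sided Fisher exact test" (SAP 3.7). Treated: "with twelve (12) children receiving Dose B" (SAP 3.7). Controls: "This comparison cohort encompasses all 51 patients enrolled in the PNCR study" meeting the listed criteria (SAP 5.6.1). Standing: "7/51 (14%) of the natural history cohort attained the ability to stand alone"; walking 5/51 (10%). Expected treated rates: 85% standing, 60% walking (SAP 3.7).

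**Assumptions not in the documents.** Onset uniform over 12 months; probability *d* of showing the skill at each visit, 0.5 to 1.0, independent between visits; skill lasting, or present for 3 months or 1 month only.

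**1. The plan's own figure.** Enumerating all outcomes of 12 v 51 under the two-sided Fisher test gives power of 99.9% for 85% v 14% and 94.3% for 60% v 10%. The claim of more than 90% reproduces.

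**2. Dates (Cox).** For a lasting skill shown at every visit, the mean delay is the sum of (gap²/2) over the gaps, divided by 12.
- Monthly: 12 × (1²/2) / 12 = 0.5 month.
- PNCR, gaps 2, 2, 2, 3, 3: (2 + 2 + 2 + 4.5 + 4.5) / 12 = 1.25 months.

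The difference is 0.75 month with no missed detection at all. Family video can only shorten the treated delay.

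**3. Proportions.** A lasting skill with *k* visits left is captured with probability 1 − (1 − *d*)^*k*, averaged over onset. At *d* = 0.5:
- Monthly: 1 − (sum of 0.5^*k*, *k* = 1 to 12) / 12 = 92%.
- PNCR: 1 − [2(0.5⁵) + 2(0.5⁴) + 2(0.5³) + 3(0.5²) + 3(0.5)] / 12 = 1 − 2.6875/12 = 78%.

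The last column is the chance of a significant result favouring AVXS-101 when both true rates are 14%.

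| Skill | *d* | Treated | PNCR | False positive |
|---|---|---|---|---|
| Lasting | 1.0 | 100% | 100% | 2.3% |
| Lasting | 0.9 | 99% | 97% | 2.4% |
| Lasting | 0.7 | 96% | 90% | 2.8% |
| Lasting | 0.5 | 92% | 78% | 3.7% |
| 3 months | 0.7 | 95% | 74% | 4.6% |
| 3 months | 0.5 | 83% | 54% | 6.3% |
| 1 month (extreme) | 1.0 | 100% | 42% | 14.4% |

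**4. Re-mapped PNCR child.** With looks at Months 2, 5 and 8, a lasting skill shown at every visit is captured only if gained by Month 8: 8/12 = 67%, against 100% on monthly visits. The documents do not say how many children are re-mapped.

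**5. Power with equal capture.** Divide the PNCR rate by the capture ratio (PNCR/treated). For a lasting skill at *d* = 0.5 the ratio is 0.847, so 14% becomes 16.5%; power is 99.8% for standing and 91.6% for walking. For a 3-month skill at *d* = 0.5, walking power is 84.4%. In the 1-month extreme, standing is 90.2% and walking 61.7%.

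**6. Observed results.** Near the planned effect the conclusion is robust. Standing at 10/12 stays significant up to 24/51 (p=0.028; 25/51 gives 0.051). Walking at 7/12 stays significant up to 13/51 (p=0.040; 14/51 gives 0.085). At smaller effects it is not:
- Standing: 5/12 v 7/51, p=0.041; 4/12 v 7/51, p=0.197; 5/12 v 8/51, p=0.105.
- Walking: 5/12 v 5/51, p=0.016; 4/12 v 5/51, p=0.058.

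The older group's walking comparison has the same asymmetry but was not quantified.

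**The case against.** A reader might infer that the primary standing result is biased towards AVXS-101 overall, or that the power claim fails. The documents do not support either reading.

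- Both sources have a Month 12 visit and the proportion is cumulative, so a lasting, reliably shown skill is captured equally.
- PNCR children have six scoring occasions, because Baseline counts. SAP 5.6.1 states 7/51 and 5/51 without a 12-month limit.
- Every treated milestone must pass independent central video review; none is described for PNCR.
- Children who have ever stood are excluded from treatment (Protocol 8.2, criterion 1). SAP 5.6.1 states no such exclusion for the younger PNCR set and admits children first seen by 36 months.
- The per-visit detection values are assumptions, and the Cox model for standing is only supportive.

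All of this stands, and it leaves the net direction open. Two things survive. Baseline credit adds no chance of catching a skill gained during follow-up, and neither it nor central review changes the later detection built into the PNCR visit schedule.

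**Conclusion.** The asymmetry is documented and unaddressed, and taken alone it can only favour AVXS-101. In the Cox comparisons it needs no missed detection: 0.5 against 1.25 months' mean delay, assuming uniform onset. In the 12-month proportions it needs a missed or transient skill, or missing or re-mapped PNCR visits. For a lasting skill the one-directional false-positive rate then moves from 2.3% to at most 3.7% over the detection values tried; only short-lived skills give more.

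The size cannot be fixed from the documents, which give neither per-visit detection, nor PNCR attendance, nor the number of milestones seen only on family video. The net direction across all features is not established. The stated power is correct for the rates on which it is based, and a result near the planned effect would stand. A borderline result could turn on one child, which is reason enough to specify the check in advance.

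**What to change.** Add to SAP 8.1.1 and 8.2.1 one sensitivity analysis with three parts:

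- **(a) Proportions.** Exclude milestones resting on family video alone and repeat the Fisher test and confidence interval on clinic-visit evidence. Carry forward as attained any milestone first shown at any clinic visit up to Month 12, in line with Protocol 11.2.
- **(b) Time to event.** Move each treated attainment date to the next PNCR visit month (2, 4, 6, 9 or 12), or fit an interval-censored model in both groups. Under the assumptions of step 2, moving the clinic-visit dates gives both groups a mean delay of 1.25 months.
- **(c) Reporting.** State how many milestones rest on family video alone.

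Reconcile the dating rules in Protocol 11.2 and 11.3 before (b) is programmed.

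Treated demonstrations should not be restricted to the Month 2, 4, 6, 9 and 12 windows. Because attained items need not be repeated, a child first filmed at another visit could be scored a failure. With perfect detection and no repetition, only 5/12 = 42% of treated achievers would count, turning 10/12 into about 4/12.

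Part (a) has limits. It leaves monthly visits set against the PNCR schedule, and it may drop a child shown at home and never re-filmed in clinic.

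The cost is one extra table per endpoint, and the treated rate or hazard ratio may be somewhat less favourable. The primary analysis is unchanged.

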## 12. ASSESSMENT OF SAFETY

### 12.1. Safety Parameters

The primary outcome for this clinical trial is safety. Study discontinuation rules are based on the development of unacceptable toxicity, defined as the occurrence of any one Grade III or higher treatment-related toxicity.

#### 12.1.1. Dose Limiting Toxicity

Dose limiting toxicity is defined as any grade III AE, according to the CTCAE version 4.03 that is possibly, probably or definitely related to the study agent. The CTCAE version 4.03 classifications are outlined in [Table 6](#).

**Table 6: Common Terminology Criteria for Adverse Events**

Grade	Definition
1	Mild; asymptomatic or mild symptoms; clinical or diagnostic observations only; intervention not indicated
2	Moderate; minimal, local or noninvasive intervention indicated; limiting age appropriate instrumental ADL. a
3	Severe or medically significant, but not immediately life-threatening; hospitalization or prolongation of hospitalization indicated; disabling; limiting selfcare ADL. b
4	Life-threatening consequences; urgent intervention indicated.
5	Death related to AE.

Source: Common Terminology Criteria for Adverse Events (version 4.03)

a Instrumental ADL refer to preparing meals, shopping for groceries or clothes, using the telephone, managing money, etc.

b Self-care ADL refer to bathing, dressing and undressing, feeding self, using the toilet, taking medications, and not bedridden.

Study enrollment will be interrupted by the Investigators when any patient experiences a Grade III, or higher AE toxicity that is unanticipated and possibly, probably, or definitely related to the study product. The event will then be reviewed by the DSMB/DMC and an evaluation will be made as to whether the trial should be terminated early following the discontinuation rules.

Dose limiting toxicities must be immediately reported as per study safety reporting guidelines to ensure timely escalation to the DSMB/DMC.

#### 12.1.2. Discontinuation Rules

An independent DSMB/DMC and medical monitor will monitor safety data on a continual basis throughout the trial. The DSMB/DMC can recommend early termination of the trial for reasons of safety. Study enrollment will be halted by the Investigators when any patient experiences a Grade III, or higher AE toxicity that is unanticipated and possibly, probably, or definitely related to the study product that presents with clinical symptoms and requires medical treatment. This will include any patient death, important clinical laboratory finding, or any severe local complication in the injected area related to administration of the study agent. If after review by

the DSMB/DMC the decision is made to continue, the study will proceed according to [Section 7.1](#) of this protocol.

## 12.2. Demographic/Medical History

Patient demographics and medical history information will be collected at baseline and captured in the eCRF. Medical history throughout the study will be collected as a Review of Systems at each visit.

Medical History information will include:

- Familial history of SMA including affected siblings or parent carriers;
- Gestational age at birth;
- Length/height/head circumference at birth;
- Hospitalization information from time of birth including number, duration, and reason for hospitalizations including International Statistical Classification of Diseases and Related Health Problems (ICD-10) codes if available;
- Historical ventilatory support, if any;
- Historical feeding support, if any

## 12.3. Vital Signs

Vital signs will include blood pressure, respiratory rate, pulse, and axillary temperature within 30 days of dosing and at the time points specified in [Table 3](#).

Vitals including pulse oximetry and heart rate will be continuously monitored and recorded by a team member during the injection.

After patients are admitted, vitals including blood pressure, respiratory rate, pulse axillary temperature, pulse oximetry, and heart rate will be monitored and recorded every 15 minutes ( $\pm$  5 minutes) after dosing for four hours and every hour ( $\pm$  15 minutes) for 24 hours following the AVXS-101 dosing procedure.

## 12.4. Weight and Length/Height

Weight and length and/or height, as appropriate, will be measured as per the time points specified in [Table 3](#).

## 12.5. Physical Examination

Physical examination will include review of the following systems: head, eyes, ears, nose and throat, lungs/thorax, cardiovascular, abdomen, musculoskeletal, neurologic, dermatologic, lymphatic, and genitourinary.

The head circumference shall be measured with each physical examination. To measure head circumference, the examiner should securely wrap a flexible measuring tape around the circumference of the head, above the eyebrows over the broadest part of the forehead, above the

ears, and over the most prominent part of the occiput. The measurement should be taken 3 times, and the largest measurement should be recorded to an accuracy of 0.1 centimeters.

Baseline physical examinations must be completed within 30 days of dosing, and in accord with the time points specified in [Table 3](#).

## 12.6. Vaccination Recommendations

Patients are encouraged to follow all routinely scheduled immunizations as recommended by the Center for Disease Control (CDC) including palivizumab prophylaxis (also known as Synagis) to prevent RSV infections in accordance with the recommendations of the American Academy of Pediatrics ([AAP 2009](#)).

## 12.7. Electrocardiogram

A 12-lead electrocardiogram (ECG) will be performed as specified in the SoA ([Table 3](#)). For patients enrolled in the study prior to Amendment 5 and irrespective of study schedule, after signing an updated informed consent, all patients should have a 12-lead ECG at their next scheduled visit and then in conformity with the SoA ([Table 3](#)).

The ECG will be interpreted locally by a cardiologist or designee for immediate safety evaluation. The ECG tracings or ECG machine data will also be collected for centralized review and interpretation by a cardiologist.

A 12-Lead ECG will be performed (concurrent with Holter Monitor) as specified in the SoA ([Table 3](#)). Additional electrophysiological monitoring will be at the discretion of the Investigator as per local institutional guidelines.

## 12.8. 12-Lead Holter Monitor

Patients will have a 12-lead continuous Holter monitor attached 24 hours prior to dose administration on Day -1. The Holter monitor will remain through 48 hours (Day 3). Serial ECG data will be pulled in triplicate from the Holter monitor data at the following time points:

- pre-dose
- 2 hour
- 4 hour
- 6 hour
- 8 hour
- 12 hour
- 24 hour
- 36 hour
- 48 hour

Twenty-four-hour Holter monitoring will also be performed as specified in the SoA ([Table 3](#)). For patients enrolled in the study prior to Amendment 5 and irrespective of study schedule, after signing an updated informed consent, patients should have a 24-hour Holter monitor at their next scheduled visit and then in conformity with the SoA.

Holter monitors will be provided to study sites along with a dedicated laptop for uploading the data from the memory cards for centralized review and analysis by a cardiologist within 24 hours of data upload. AveXis will be notified of any safety concerns from the centralized review.

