**Table 3: Schedule of Assessments**

Study Interval	Baseline Screening	Vector (AVXS-101) Injection (Inpatient)		Follow-up (Outpatient)										Notes		
		Study Day	Window	-60 to -2	-1	1	2-3	7	14	21	30	44	60	72	Monthly Through M12 	M15/ EOS
Informed Consent	X							± 2				± 7				
Spinal X-ray	X															
Demographics/ Medical History	X		X	(X)	X	X	X	X			X		X	X	Medical history collected at baseline; review of systems conducted at each study visit. (X): Patients to remain inpatient 48 hours post-dose for observation and AE monitoring.	
Physical Exam	(X)		X	X	X	X	X	X			X		X	X	Includes measuring head circumference. (X): Baseline procedure must be completed within 30 days of dosing.	
Vitals/Weight/ Length/Height	(X)		X	X	X	X	X	X			X		X	X	Vital signs will include BP, respiratory rate, pulse, and axillary temperature. Vitals including BP, respiratory rate, pulse axillary temperature, pulse oximetry and HR will be monitored and recorded every 15 minutes (± 5 minutes) from dosing for four hours and every hour (± 15 minutes) for 24 hours following the AVXS-101 dosing procedure. (X): Baseline procedure must be completed within 30 days of dosing.	
Pulse Oximetry	(X)		X	X	X	X	X	X			X		X	X	(X): Baseline procedure must be completed within 30 days of dosing.	
Pulmonary Exam	(X)								X		X		X	X		

 Patients who reached the Month 12 visit prior to Protocol Amendment 7 had their EOS assessments conducted at Month 12.

Study Interval	Baseline Screening	Vector (AVXS-101) Injection (Inpatient)			Follow-up (Outpatient)										Notes
		-1	1	2-3	7	14	21	30	44	60	72	Monthly Through M12 	M15/ EOS		
Study Day	-60 to -2														
Window					± 2					± 7					
12-Lead ECG	X		X	X								(X)	X	Irrespective of study schedule, after signing the updated informed consent, all patients enrolled prior to the Amendment 5 version of the protocol should have ECG, 24-hour Holter monitoring, and echocardiogram done at the next scheduled visit and then in conformity with the study SoA. (X): Months 3, 6, 9, and 12 visits.	
12-Lead Holter Monitor	X	X	X	X			X		(X)		(X)	X		ECGs extracted from Holter by central reader in triplicate at the following time points: pre-dose, 2h, 4h, 6h, 8h, 12h, 24h, 36h, and 48h during the patient's inpatient stay. (X): Months 2, 3, 6, 9, and 12 visits.	

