### 11.4.2. Statistical Methods

Clinical laboratory tests at each scheduled visit will be summarized overall and by actual dose received and age group. The baseline value will be the last measurement on or before the day of the injection of study product. Mean changes from baseline to each post-baseline visit will be summarized for each protocol-specified hematology, clinical chemistry, coagulation, and capillary blood gas laboratory parameter with the baseline mean, visit mean, change from baseline mean, standard deviation, minimum, maximum, and median.

Immunology and virus serology data will be summarized using descriptive statistics appropriate for categorical variables (i.e. number and percentage of patients with each reported result at each visit). Urinalysis data will only be presented in listings.

Chemistry, hematology, and coagulation laboratory data values will be categorized as low, normal, or high based on normal ranges of the laboratory used in this study. Shift tables from baseline to minimum value, maximum value, and final treatment values will be created. The shift tables will cross tabulate the frequency of patients with baseline values below/within/above the normal range versus minimum/maximum/final values below/within/above the normal range.

The number and percentage of patients with post-baseline values meeting the specified criteria for PCS laboratory values will be summarized overall and by actual dose received and age group. A post-baseline value must be more extreme than the baseline value to be considered a PCS finding. A listing will be provided to present the entire set of lab values for a patient for the parameter meeting PCS criteria during treatment.

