## 11.7. 12-Lead Holter Monitor

Patients will have a 12-lead continuous Holter monitor attached 24 hours prior to dose administration on Day -1 and the Holter will remain in place through 48 hours post-dose (Day 3). Serial ECG data from Holter monitor will be pulled in triplicate at time points of 'pre-dose', '2 hour', '4 hour', '6 hour', '8 hour', '12 hour', '24 hour', '36 hour' and '48 hour' post-dose and assessed by a central reviewer. The triplicate of each parameter for HR, PR, QRS, QTcF, as measured by the central reviewer, at each time point will be averaged for summaries. The summaries of Holter monitor data will be done by the actual treatment received overall and by dose and age group.

Twenty-four-hour Holter monitoring will also be performed as per the Schedule of Assessments.

The central reviewer will identify abnormal ECGs that are PCS based on central reviewing guidelines provided by BMS. The number and percent of patients meeting each PCS criterion will be summarized starting at '2 hour' and continuing through '48 hour'.

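### SAP 11.7 counts potentially significant Holter findings only after dosing, with no pre-dose count and no new-or-worsened rule, so an abnormality already present can be tabulated as a post-dose finding

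*Protocol*

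**What the plan says.** Protocol 12.8 starts the Holter a day before treatment: "Patients will have a 12-lead continuous Holter monitor attached 24 hours prior to dose administration on Day -1". The monitor stays on until 48 hours after dosing. The extraction rule is "Serial ECG data will be pulled in triplicate from the Holter monitor data at the following time points", and the list that follows has one pre-dose entry and eight post-dose entries. The Schedule of Assessments (Protocol Table 3) gives the same nine times: "pre-dose, 2h, 4h, 6h, 8h, 12h, 24h, 36h, and 48h during the patient's inpatient stay".

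SAP 11.7 covers the analysis in two steps. For HR, PR, QRS and QTcF, the triplicate "at each time point will be averaged for summaries"; the pre-dose time is among those listed, so it appears in the descriptive summaries. For PCS findings the rule is: "The number and percent of patients meeting each PCS criterion will be summarized starting at '2 hour' and continuing through '48 hour". The criteria come from a central-reader guideline held outside the SAP. The section does not mention change from the pre-dose value, a shift table, or the child's pre-dose PCS status.

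For laboratory values, SAP 11.4.2 does set a condition: "A post-baseline value must be more extreme than the baseline value to be considered a PCS finding".

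**The concern.** The trial is single-arm within each dose. SAP 11 states that safety data, Holter data included, will not be compared with the PNCR cohort. The reference for an early cardiac finding therefore has to come from the child's own earlier recordings. A pre-dose triplicate is extracted for every child, but the PCS count does not use it.

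Followed as written, the table cannot separate a child whose tracing became abnormal after dosing from one whose tracing was abnormal already. That distinction matters because Protocol 5.5 describes cardiac toxicity in mice, SAP 11.3.2.4 lists cardiac events as adverse events of special interest, and the groups are small enough for one child to move a percentage visibly.

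**Working it through.** The documents give no sample size, power or error rate for Holter findings, so there is no stated figure to reproduce. The check is a comparison of rules, followed by simple arithmetic.

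**1. Rules side by side**

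| Data | Baseline handling in the SAP |
|---|---|
| Laboratory PCS (11.4.2) | Must be more extreme than baseline |
| 12-lead ECG intervals (11.6) | Mean change from baseline |
| Vital signs (11.5) | Mean change from baseline at each visit and time point; PCS count has no baseline condition |
| Adverse events (11.3.1) | Must begin or worsen after injection |
| Holter intervals (11.7) | Triplicates averaged per time point; no change from pre-dose |
| Holter PCS (11.7) | Counted from 2 to 48 hours; no pre-dose count and no condition |

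The general text does not fill the gap. SAP 6.5 says all values are considered for potentially significant values. The baseline is also not unique: SAP 6.2.1 uses the last assessment before dose, whereas SAP 6.5 uses the latest value before Day 1. A pre-dose Holter reading taken on the morning of Day 1 qualifies under the first and not under the second. SAP 11.7 does not choose.

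**2. Size for one child with a persistent pre-existing abnormality**

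Input: 12 children per age group planned at Dose B (Protocol 7.1). Such a child is counted at all eight post-dose times.

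- Contribution at each time: 1/12 = 8.3%.
- SAP 11.7 also tabulates by dose and age group. In Cohort 1, with 3 planned children, one child is 1/3 = 33.3%. Among the 4 children treated in Cohort 3 (SAP 2.2.1), one child is 1/4 = 25.0%.

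**3. How likely is at least one such child among 12?**

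The prevalence q is not in the documents, so it is an assumption. P(at least one) = 1 − (1 − q)^12.

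- q = 2%: 1 − 0.98^12 = 21.5%
- q = 5%: 1 − 0.95^12 = 46.0%
- q = 10%: 1 − 0.90^12 = 71.8%

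**4. Time of day**

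Take the pre-dose reading as just before dosing, and each nominal hour modulo 24. The 24 and 48 hour readings fall at the same clock time as the pre-dose reading. The 2, 4, 6, 8, 12 and 36 hour readings do not, so six of eight are unmatched. The 24-hour pre-dose recording contains the matching times: −22, −20, −18 and −16 hours for 2, 4, 6 and 8 hours, and −12 hours for both 12 and 36 hours.

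**5. What one pre-dose reading can remove**

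A new-or-worsened rule based on the single pre-dose triplicate removes persistent abnormalities. It does little for intermittent ones. Assume a background flag rate p per reading, independent across readings. The share of children flagged at least once in eight readings is 1 − (1 − p)^8; excluding children flagged pre-dose multiplies this by (1 − p).

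- p = 2%: 14.9% becomes 0.98 × 14.9% = 14.6%
- p = 5%: 33.7% becomes 0.95 × 33.7% = 32.0%

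This is the reason to consider further pre-dose readings, as an option.

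**The case against.** The case for leaving the text alone has several parts.

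- **The external guideline may already handle it.** PCS status is judged under a document not available here, which could contain a change-from-baseline criterion. This stands: the documents support only that pre-existing findings can appear, not that they will. The SAP should still state the rule, since it defines the table.
- **Unconditional counting is common in this SAP and is cautious.** Vital-sign PCS counts have no baseline condition, and the liver thresholds in SAP 11.4.2 apply regardless of baseline. Such counting over-flags rather than hides a signal. This also stands, and it is why the unconditional count should be kept, with the new-or-worsened count beside it.
- **The consequences are narrow.** Adverse event tables require onset or worsening after injection, cardiac events of special interest are drawn from those, SAP 13 says the SAP's safety analysis is not planned for the DSMB, and a cardiologist reviews uploaded Holter data centrally. All of this is correct.

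A reader might also infer more than the documents support:

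- That the first 48 hours have no other time course. SAP 11.5 summarises change from baseline by time point for vital signs, including heart rate. What remains is that SAP 11.6 describes 12-lead ECG interval changes to the end-of-study visit, so it gives no hourly course for PR, QRS or QTcF.
- That the Day -1 recording is the only available reference. A Holter and a 12-lead ECG are also scheduled at screening.
- That the pre-dose reading is ignored. It enters the descriptive summaries; it is absent from the PCS count.
- That time of day confounds every reading. The 24 and 48 hour readings are nominally matched.
- That shares such as 14.9% or 33.7% measure the problem. They describe repeated looks under assumed independence and an any-time count, which the SAP does not specify, and step 5 shows that a pre-dose rule barely changes them.

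**Conclusion.** The point holds for one descriptive table. As SAP 11.7 is written, the Holter PCS table has no pre-dose column and no new-or-worsened condition, so a pre-existing abnormality can be read as a post-dose finding. The size is 8.3 percentage points per affected child at every post-dose time in a group of 12, and more in the smaller cohorts. How often this happens depends on a prevalence that the documents do not give, and on a reader guideline that they do not contain. Dose escalation and adverse event reporting are not affected. This is a low-priority improvement, worth making because the necessary reading is already extracted.

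**What to change.** In SAP 11.7:

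1. Define the Holter baseline as the mean of the pre-dose triplicate.
2. Summarise HR, PR, QRS and QTcF at each time point as observed value and change from pre-dose.
3. Show the pre-dose PCS count in the same table.
4. Beside the unconditional post-dose count, report the number of children whose finding was absent or less extreme pre-dose.
5. State whether counts are per time point or at any time from 2 to 48 hours.

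The cost is SAP wording and table programming on readings already extracted, with no burden for any child.

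Optionally, in Protocol 12.8, extract five more triplicates from the existing recording, at −22, −20, −18, −16 and −12 hours, as clock-matched references for the 2, 4, 6, 8, 12 and 36 hour points. This adds central-reader work. Clock matching does not remove residual sedation at 2 hours, which should be footnoted.
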